3. METHODS

3.1. Study setting

The trial drug will be dispensed to participants to be administered by the parent/caregiver at home. Parents/caregivers of children with complex health issues are intimately familiar with these patients' daily routines and skilled at their care and can therefore be expected to administer the study drug according to protocol.

3.2. Eligibility criteria

Inclusion criteria:

- 1) Any gender; 3 to 18 years old, inclusively
- 2) Gross Motor Functional Classification System (GMFCS53,54) score of 3, 4 or 5
- 3) Communication Function Classification System (CFCS55) level 4 or 5
- 4) A score C, D or E on the Pain Survey
- 5) Evidence of an evaluation using the PIUO Pathway showing no evidence for treatable sources (nociceptive-inflammatory) of pain and/or irritability symptoms

It is expected that most or all of the participants will be recruited from the participant cohort for the PIUO Study. If the child did not participate in the PIUO Study and has not undergone an evaluation using the PIUO Pathway, but is otherwise eligible, they may first go through the PIUO Pathway and may continue with the gabapentin trial if no evidence for sources of treatable pain are uncovered.

Exclusion criteria:

- 1) Patients with a known hypersensitivity/allergy to the study medication
- 2) Patients who are actively participating in another experimental therapy study for pain and/or irritability
- 3) Patients who are a poor medical risk because of other systemic diseases or active uncontrolled infections
- 4) Participants whose pain and or irritability is diagnosed through completion of the PIUO Pathway during the enrollment phase of the trial
- 5) Patients who score A or B on the Pain Survey
- 6) Patients who have an active source of nociceptive-inflammatory pain at the time of enrolment (e.g., post-operative pain)
- 7) Patients with active renal disease, known renal impairment or glomerular filtration rate < 60 mL/min/1.73 m2 (if known).
- 8) Patients with known significant hepatic impairment at the discretion of the investigator.
- 9) Patients with clinically relevant abnormal ECG (if available) at the discretion of the investigator.
- 10) Patients with diagnosis of sickle cell disease.

3.3. Interventions

Investigational Product Specifications

Generic Name: Gabapentin. Marketed Name: Teva-Gabapentin, DIN 02244515 (400 mg capsules)

Gabapentin readily enters the brain and prevents seizures in a number of animal models of epilepsy. Gabapentin is structurally related to the neurotransmitter GABA (gamma-aminobutyric acid) but does not possess affinity for either GABAA or GABAB receptor.

Gabapentin binds with high affinity to the α 2- δ (alpha-2-delta) subunit of voltage-gated calcium channels. Broad panel screening suggests it does not bind to other neurotransmitter receptors of the brain and does not interact with sodium channels.

Formulation, Storage and Handling

Teva-Gabapentin (gabapentin) 400 mg capsules contain gabapentin, colloidal silicon dioxide, lactose monohydrate, pregelatinized starch, and talc. Capsule shells may contain gelatin, titanium dioxide, yellow iron oxide, red iron oxide and blue ink.

Store capsules at room temperature between 15-30°C.

For each study participant, 400 mg capsules will be compounded with OraPlus and OraSweet Sugar Free in a 1:1 ratio to create a 100 mg/mL oral liquid by the study site pharmacy. Similar-ly, placebo bottles will be prepared containing the same amount of OraPlus and OraSweet Sug-ar Free. The drug will be dispensed shortly after preparation.

The 100 mg/mL oral liquid will be supplied in bottles and should be stored at room temperature between 15-30°C.

OraPlus and OraSweet Sugar Free are recommended as the compound solutions acceptable for all participants, including those with diabetes. For participants on a ketogenic diet it will be confirmed with the Neurological Care Centre, Ketogenic Diet program at BC Children's Hospital that the amount of OraPlus and OraSweet Sugar Free they will receive is safe, prior to dispensing ([name] RD, personal communication, May 25th 2020)

Supply and Accountability

Teva-Gabapentin (gabapentin) 400 mg capsules are supplied as orange opaque cap and body hard gelatin capsules, size #0, with N and "400" printed in blue ink on opposing cap and body portions of the capsules.

Labeled and compounded 100 mg/mL study drug bottles will be supplied by the BC Children's Hospital pharmacy to study participants and drug accountability will be conducted by the same pharmacist.

Regimen, Administration and Duration

Summary: This study uses a rapid and safe dose escalation to the widely accepted therapeutic range where evaluation of response will be undertaken with frequent scoring. Different maximal doses are used for children < or ≥ 15 kg, based on pharmacokinetic data. Doses are titrated to clinical effect or maximum target dose, whichever is lower. Once in the therapeutic range, doses change after 3 days if there is not an adequate reduction in symptoms. For any subject that obtains clinical benefit below maximal dose, then they will be held at that dose for the remainder of that period until such time as the scheduled wean begins. At the end of each treatment period there is a wash-out.

Starting Dose: The starting dose of gabapentin will be 5 mg/kg administered as oral liquid or via gastric or jejunal routes. On Day 1 of the study, the gabapentin will be administered once at bed-time and then increased according to the schedule shown in Table 1.

Dose Escalation: The dose will be increased every 3^{rd} - 4^{th} day in a step wise fashion of 13% - 50%, starting with the evening dose in order to accommodate sedation. The maximum dose for subjects will be as follows: < 15 kg to 60 mg/kg day and \geq 15 kg to 45 mg/kg/day. Dose titration will be to a maximum target dose (based on weight as described, < 15 kg, > 15kg) or to clinical effect, whichever is lower. The dose escalation scheme is based upon expert consensus and personal communication with [name], [name], and upon review with the BC Children's Hospital research pharmacist. \cdot , 56.

Some children with PIUO and SNI have been given gabapentin empirically by their health care provider, often without any subsequent, detailed assessment of benefit. Many times, the medication is continued because of its low side-effect profile and overall safety compared with other analgesics. If a subject is currently on gabapentin at the time of enrolment, and the parent/caregiver wants an evaluation of its effectiveness, then the subject can be enrolled in this study with the following approach:

After appropriate enrolment and consent, the subject will be weaned off of gabapentin, in a stepwise manner with 25% reductions in dose every 3rd day. Once they are no longer on the active drug, they will be randomized to active drug or placebo like all other study participants.

Gabapentin Risks and Precautions

Risk minimization, management, and assessment procedures have been implemented in the study to minimize and assess potential risks to participants who participate in this clinical study with gabapentin. Components include: (1) specific study eligibility and exclusion criteria to ensure that participants who have underlying characteristics that potentially increase their risk for an adverse outcome are excluded. These include patients with a history of previous sensitivity to gabapentin. (2) Protocol-specific procedures for minimizing and managing AEs: sedation is the most common AE to gabapentin, and we will address this by titrating upwards on the dose every 3rd day, and always increasing the nighttime dose first; (3) overview surveillance by the independent Data Safety Monitoring Board; (4) ongoing follow-up throughout the study by research personnel twice weekly, coinciding with dose increases to check for AE as shown in the table below.

Refer to the TEVA-Gabapentin (gabapentin) TEVA Canada Product Monograph (DIN 02244515) for a detailed description of warnings, precautions, and adverse events: https://health-products.canada.ca/dpd-bdpp/info.do?lang=en&code=68492

The following potential side effects occurred in clinical trials across ages 3-adults at rates higher than in placebo groups:

- Somnolence
- Dizziness
- Fatigue
- Nausea and/or Vomiting
- Increase Weight
- Emotional Lability
- Hostility
- Hyperkinesia
- Respiratory Infection
- Fever
- Swelling of limbs
- Gait disturbance

Implementation and adherence

The participant's parent or primary caregiver will administer the drug and track drug administration daily. They will be aided by written and verbal instructions by the pharmacist to dispense the correct dosage at the correct intervals. This counselling by the study pharmacist will take place in person, on site at the Baseline Visit. Adherence to the protocol will be accounted for via a daily tracker and measurement of drug use by the pharmacist. Participants will be pro-vided with the daily tracker to guide them administer the correct drug dose and will be instructed in using the tracker at every drug administration. Upon completing the Sequence 1 and Sequence 2 participants will be instructed to return the bottles containing gabapentin or placebo and the pharmacist will measure the leftover drug against what was originally dispensed. In or-der to lessen the burden on study participants and ensure a timely return of the bottles, a secure courier service will be offered to participants who would be inconvenienced by returning the bottles to the study site.

Concealment mechanism

Both active drug and placebo will be masked in a liquid formulation, and administered via the same route (oral, direct gastric route, or direct jejunal route) depending on the subject's usual feeding approach. The label applied to the bottle will be blinded by the Research Pharmacy and identical flavouring will be added to the drug and placebo for additional masking.

Concomitant Care

Participants may receive any concomitant care, including medications, they wish during the trial. Due to their medical complexity it is expected that most participants will be doing so. Of specific consideration are:

 Aluminum and magnesium-based antacids reduce gabapentin bioavailability up to 20% (PrTEVA-GABAPENTIN Product Monograph (Capsules 100 mg, 300 mg, and 400 mg Tablets 600 mg and 800 mg). Part III Consumer Information p. 29 Serious Warnings and Precautions. Teva Canada Limited. Date of Revision: August 25, 2020. Available at: https://www.tevacanada.com/globalassets/canada-ph2/product-monographs/gabapentine-capsules-100-300-400-tablets-600-800mg-teva-pm-aug25_2020-wis-eng.pdf. Accessed October 4, 2020). It is uncommon in the patient population and no patients will be on A1 or Mg containing antacids.

The risk of serious side effects of respiratory depression with concomitant use with opioids is acknowledged (BC Children's Hospital Integrated Pain Service Gabapentin Information http://www.bcchildrens.ca/Pain-Services-Site/Docu-Sheet. Accessed at: ments/BCCH1455Gabapentin.pdf. Retrieved on October 4, 2020). A minority of patients might be on opioids. Dose adjustments will be added when gabapentin is used with a concomitant opioid or other CNS depressant medication: the family will be advised to return to the previous stable, safe dose in the protocol, and the subject will remain at that dose with no further escalation for the duration of the trial arm. This schedule will be duplicated on the parallel arm (active drug or placebo) to maintain masking. The participants are highly monitored, often with continuous oxygen saturation monitoring and/or "baby-cam" devices observing them during sleep. During the daytime they are with family, or professional caregivers (aides, nurses, etc.). These individuals will be advised to watch for respiratory depression and sedation that occur well before fatal apnea, and how to respond.

While there are no prohibitions on concomitant care, any care or medications unrelated to the trial will be noted in the CRFs for each participant.

Participants are sometimes obtaining respite care at facilities with nursing and physician care. Medical reconciliation is done at each admission. Parents will be provided with a letter to share with these programs outlining the study, the drug being tested, and a 24-hour pager to contact for further information or concerns

Active Participants < 15kg in mg per kg

Day	Morning mg/kg	Noon mg/kg	Evening mg/kg	Total mg/kg per day	% Change
1*	0	0	5	5	0
2	0	5	5	10	100%
3	5	5	5	15	50%
4	5	5	5	15	0%
5	5	5	10	20	33%
6	5	5	10	20	0%
7	5	5	10	20	0%
8	10	10	10	30	50%
9	10	10	10	30	0%
10	10	10	10	30	0%
11	13.3	13.3	13.3	40	33%
12	13.3	13.3	13.3	40	0%
13	13.3	13.3	13.3	40	0%
14	17	17	17	50	25%
15	17	17	17	50	0%
16	17	17	17	50	0%
17	20	20	20	60	20%
18	20	20	20	60	0%
19	20	20	20	60	0%
20	13.3	13.3	13.3	40	-33%
21	6.7	6.7	6.7	20	-50%
22	0	5	5	10	-50%
23	0	0	5	5	-50%
24	0	0	0	0	-100%
25	0	0	0	0	0%
Switch over*	-	-	-	-	-

^{*}Day one or 26 if switching over, not both.

Active Participants > = 15kg in mg per day

Day	Morning mg	Noon mg	Evening mg	Total mg/kg per day	Total mg/day	% Change
1*	0	0	75	5	75	0
2	0	75	75	10	150	100%
3	75	75	75	15	225	50%
4	75	75	75	15	225	0%
5	100	100	100	20	300	33%
6	100	100	100	20	300	0%
7	100	100	100	20	300	0%
8	150	150	150	30	450	50%
9	150	150	150	30	450	0%
10	150	150	150	30	450	0%
11	200	200	200	40	600	33%
12	200	200	200	40	600	0%
13	200	200	200	40	600	0%
14	225	225	225	45	675	13%
15	225	225	225	45	675	0%
16	225	225	225	45	675	0%
17	225	225	225	45	675	0%
18	150	150	150	30	450	-33%
19	150	150	150	30	450	0%
20	100	100	100	20	300	-33%
21	100	100	100	20	300	0%
22	50	50	50	10	150	-50%
23	25	25	25	5	75	-50%
24	0	0	0	0	0	-100%
25	0	0	0	0	0	0%
Switch over*	_	-	-	-	_	-

^{*}Day one or 26 if switching over, not both.

Inactive

Day	Morning mg/kg	Noon mg/kg	Evening mg/kg	Total mg/kg per day	% Change
1*	0	0	0	0	0%
2	0	0	0	0	0%
3	0	0	0	0	0%
4	0	0	0	0	0%
5	0	0	0	0	0%
6	0	0	0	0	0%
7	0	0	0	0	0%
8	0	0	0	0	0%
9	0	0	0	0	0%
10	0	0	0	0	0%
11	0	0	0	0	0%
12	0	0	0	0	0%
13	0	0	0	0	0%
14	0	0	0	0	0%
15	0	0	0	0	0%
16	0	0	0	0	0%
17	0	0	0	0	0%
18	0	0	0	0	0%
19	0	0	0	0	0%
20	0	0	0	0	0%
21	0	0	0	0	0%
22	0	0	0	0	0%
23	0	0	0	0	0%
24	0	0	0	0	0%
25	0	0	0	0	0%
Switch over*	0	0	0	0	0%

^{*}Day one or 26 if switching over, not both.

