2.2. Objectives

The primary objective of the trial is to evaluate the effectiveness of gabapentin to decrease pain and irritability in children with SNI, when the source of pain and irritability is attributed to neurological dysregulation (nociplastic pain), as measured by parent reported pain scores. This objective corresponds to the primary outcome listed in section 3.4.1.

We will compare the gabapentin versus placebo along an escalating dose range for both individual subjects and for the group. We will aggregate the results of the completed N-of-1 trials across all subjects to estimate the group level comparative effectiveness of gabapentin in reducing pain and irritability.

The secondary objectives are to:

- 1. Identify the optimal dosing of gabapentin in reducing pain and irritability (Corresponds to secondary outcomes 3.4.2 and 3.4.3).
- 2. Identify the latency time for gabapentin to show effectiveness (Corresponds to secondary outcome 3.4.4).
- 3. Evaluate the safety and tolerability of gabapentin (Corresponds to secondary outcome 3.4.5).
- 4. An Exploratory objective will be to evaluate whether parent/caregiver stress and function improve if gabapentin reduces children's pain and irritability. This objective corresponds to the Exploratory outcome listed in section 3.4.6.

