2.3. Trial Design

With the small sample size and time needed to titrate up to an effective dose, this trial proposes to use a single randomized multiple-measures cross-over design (N-of-1), with results aggregated over several subjects. This design is well-suited to outcomes that are highly specific to each individual and not amenable to precise measurement across a large cohort. The heterogenous nature

of pain and irritability responses in children are more likely to be personally specific and characteristic, rather than generalizable. The behavioural pattern is reflected in the structure of the standard tools for pain assessment in SNI that rely upon a catalogue of behaviour patterns that differ from one child to the next.^{3,29,50-52}

The proposed cross-over trial will use randomization and blinding of subjects and observers with placebo controls to reduce unexpected bias. A critical distinction is that each subject will serve as their own control and experiment, allowing for a finer assessment of the treatment efficacy within each patient.

In this trial, each patient will switch between gabapentin (G) and placebo (P). The sequence of whether G precedes P (GP) or P precedes G (PG) will be randomized by the study pharmacist, and neither the clinician nor the subject (parent/caregiver) will know the sequence.

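### The placebo as described lacks the capsule powder in the active liquid, and nothing matches the two for appearance or consistency, although the parent who gives both also scores the outcome

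*Protocol*

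**What the plan says.** **Active liquid.** Section 3.3 (Formulation, Storage and Handling) states that "400 mg capsules will be compounded with OraPlus and OraSweet Sugar Free in a 1:1 ratio to create a 100 mg/mL oral liquid". It also lists what goes in with the drug: the "capsules contain gabapentin, colloidal silicon dioxide, lactose monohydrate, pregelatinized starch, and talc".

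**Placebo.** The same paragraph says that "placebo bottles will be prepared containing the same amount of OraPlus and OraSweet" Sugar Free. No filler, capsule excipient or other powder is named.

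**Masking.** Section 3.3 (Concealment mechanism) says: "Both active drug and placebo will be masked in a liquid formulation, and administered via the same route". The pharmacy blinds the label, and "identical flavouring will be added to the drug and placebo for additional masking".

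**Who handles and who scores.** Under Implementation and adherence: "The participant's parent or primary caregiver will administer the drug and track drug administration daily". Section 2.2 defines the primary objective "as measured by parent reported pain scores". Under the crossover in Section 2.3, every child receives both liquids in random order. Bottles go back at the end of each sequence, and the second supply is dispensed in person at the start of Sequence 2.

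**Reliance on the blind.** Section 2.3 relies on masking both subjects and observers to limit bias. Section 3.8 (Baseline Visit) warns that parents' perceptions could produce a placebo-by-proxy effect, and plans to ask families after each sequence which treatment they think was given.

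**The concern.** The stated masking covers liquid form, route, label and flavour. It does not cover what a powder may do to a liquid: make it cloudy, leave sediment or change how it draws into a syringe. Flavouring also does less for children dosed by gastric or jejunal tube. There the child's taste plays no part, and the parent's view of the liquid is the cue that remains.

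This trial is more exposed to such a cue than most. One person prepares the doses, gives them and supplies the primary score, and the protocol names no independent NCCPC-R rater. Doses are titrated to clinical effect, so a biased perception could also influence the dose reached and hence the lowest-effective-dose outcome. Each family's results are returned to help it decide about continuing gabapentin, so a bias would affect individual conclusions as well as the group mean.

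**Working it through.** The plan states no figure on this point, so there is none to reproduce. The check compares the two compositions and then asks which stated measure covers the difference.

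**1. Powder per mL of active liquid.** Inputs from Section 3.3: capsule strength 400 mg, concentration 100 mg/mL.

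- 100 / 400 = 0.25 capsule per mL.

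At the largest single dose in the dosing table for children of 15 kg or more (225 mg, three times daily, 675 mg/day):

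- Volume per dose: 225 / 100 = 2.25 mL, holding 225 / 400 = 0.56 capsule.
- Volume per day: 675 / 100 = 6.75 mL, holding 675 / 400 = 1.69 capsules.

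A placebo made exactly as described holds none of this powder.

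**2. How often the parent handles each liquid.** Section 2.3 puts drug and placebo on the same schedule. Counting non-zero entries in the active dosing tables:

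- 15 kg or more: 1 on day 1, 2 on day 2, and 3 a day on days 3 to 23 (21 days): 1 + 2 + 63 = 66 doses.
- Under 15 kg: 1 + 2, then 3 a day on days 3 to 21 (19 days, 57 doses), then 2 + 1: 63 doses.

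On the full schedule a family therefore handles each liquid more than 60 times.

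**3. Stated measures against possible cues.**

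| Possible cue | Measure in the protocol |
|---|---|
| Dosage form, route | Both liquid, same route |
| Label | Blinded by the pharmacy |
| Taste, smell | Identical flavouring in both |
| Cloudiness, colour | None stated |
| Sediment | None stated |
| Thickness | None stated |

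The document does not describe the look of either finished liquid or of the vehicle alone. It also does not say whether the coloured capsule shell is left out.

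**4. Whether the guess question protects the result.** Assume one guess per family, 10 families and a chance rate of 0.5. One-sided binomial tail probabilities:

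- P(8 or more correct) = 56/1024 = 0.055.
- P(9 or more correct) = 11/1024 = 0.011.

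At least 9 of 10 correct would be needed to fall below 0.05. If 80% of parents could truly tell, that would happen 38% of the time; if 90% could, 74%. A correct guess may also come from perceived benefit or sedation, so the question cannot isolate the appearance of the liquid. Section 3.10 does not use the answers. An analysis plan could, but detection comes after the scores have been given.

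**The case against.** The strongest reply is that distinguishability is inferred. Nothing in the document says how either liquid looks, and powder may not be noticeable in this vehicle. The Trial Summary calls the product an oral solution, which taken literally would leave nothing to see. This stands: the document supports a possible cue, not a demonstrated one.

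Second, the placebo is not bare vehicle. It has the same flavouring as the active liquid, and Section 3.3 gives a vehicle quantity rather than a full formula, so pharmacy worksheets might add matching steps. The flavouring must be acknowledged. But a protocol with its own concealment paragraph is where matched appearance would be stated, and a pharmacy following the text as written would leave the powder out.

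Third, parents never need to hold both bottles at once, because the first set is returned before the second period. That weakens any comparison, and a parent in the first sequence usually has no reference. Comparison from memory remains possible after more than 60 doses. Families already on gabapentin may enrol, although the document does not say what form they had used.

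Two stronger readings are tempting and unsupported. A reader might infer that the blind is broken; the document does not show it. A reader might also multiply an assumed share of unblinded parents by an assumed score shift and compare the product with the 11-point criterion. The document supplies neither input. The 11 points are a minimum meaningful change with a no-rebound condition, not an expected group difference between drug and placebo.

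**Conclusion.** The point holds as a weakness in the specified placebo. As written, the active liquid contains the powder of 0.25 capsule per mL that the placebo lacks, and no stated measure matches or checks appearance, sediment or thickness. Because the parent both gives the liquids and supplies the primary score, and the protocol anticipates bias through parents' perceptions, this is an unblinding cue worth removing.

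The powder difference follows directly from the text. That parents could notice it is an inference from the ingredient list. The effect on the primary contrast cannot be estimated from the document: it would be nil if the liquids are indistinguishable in practice. The planned guess question can reveal gross unblinding but does not prevent it, and with 10 families it could easily miss it. The change should be made before dispensing, because no analysis can restore a blind afterwards.

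**What to change.** Amend Section 3.3 (Formulation, Storage and Handling) so that the placebo is compounded with the inactive capsule excipients, or another matching inert powder, at the same amount per mL as the active liquid. Add to the Concealment mechanism paragraph that the pharmacy compares the two liquids for appearance, sediment and thickness, and records that they are indistinguishable before dispensing.

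The cost is a small compounding step and a check. It is not entirely free for participants, because children would receive the inert powder during the placebo period too. The ketogenic-diet safety confirmation in Section 3.3 names only OraPlus and OraSweet Sugar Free and should be extended to cover the added powder. Assessments and the dosing schedule are unaffected.

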Our work to date has developed a more efficient, focused clinical pathway to evaluate children with SNI for all potential sources of nociceptive-inflammatory ("treatable") pain. We are currently conducting a multi-site randomized, controlled trial of this clinical pathway. Our objective is to reduce the "unknown" element of pain in these children, increasing the potential for treatment. Nevertheless, there are children, who at the end of a thorough evaluation guided by a clinical pathway, will still have PIUO. These children may benefit from adjuvant analgesics such as gabapentin.

Treating with Gabapentin

According to the US FDA product information (US FDA Neurontin (gabapentin) Prescribing Information. Revised: 10/2017. Available at: https://www.accessdata.fda.gov/drugsatfda_docs/la-bel/2017/020235s064_020882s047_021129s046lbl.pdf Accessed October 4, 2020), gabapentin is indicated for adjunctive therapy in the treatment of partial onset seizures, with and without secondary generalization, in adults and pediatric patients 3 years and older with epilepsy. In Canada, however, gabapentin is authorized for use in adults only (> 18 years of age) as an antiepileptic agent and is not indicated for use in children. The precise mechanisms by which gabapentin produces its analgesic and antiepileptic actions are unknown. Gabapentin is structurally related to the neurotransmitter gamma-aminobutyric acid (GABA) but has no effect on GABA binding, uptake, or degradation. Much is known about its activity at the molecular level and there is increasing understanding that it moderates nerve signals that include pain. Gabapentin is notable for not being metabolized in humans; the parent compound is renally excreted with an elimination t1/2 of 5-7 hours.

In studies of gabapentin the main adverse effects are development of sedation and dizziness, ataxia, fatigue, and nystagmus in people 12 and older. In children aged 3-7 treated for epilepsy there was also a small increase, compared to controls of weight gain, susceptibility to viral ill ness, somnolence and hostility. (US FDA Neurontin (gabapentin) Prescribing Information. Revised: 10/2017. Available at: https://www.accessdata.fda.gov/drugsatfda_docs/la-bel/2017/020235s064_020882s047_021129s046lbl.pdf Accessed October 4, 2020),

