Gabapentin was originally developed as an anti-convulsant. In the first 10 years of its use attempts were made to find its place as a monotherapy, and later an add-on therapy, for seizures. Starting in 1996 and continuing onward there was an explosion of interest in this drug as an analgesic, especially for neuropathic and chronic, complex pain. Gabapentin is often used for these indications as it has a low adverse event profile and appears to provide clinical benefit in difficult-to-treat cases. Clinical use of gabapentin for these same indications of neuropathic and chronic pain, as well as pain and irritability, has extended to infants and children. In a longitudinal, prospective study of children with non-cancer life-threatening conditions, gabapentin was used by 13.8% of the subjects. On the subjects.

Gabapentin was tested in 118 pediatric patients age 3 to 12 years with epilepsy. This study showed that gabapentin was significantly better than placebo. The drug's pharmacokinetics were established in 48 pediatric subjects between the ages of 1 month and 12 years. The dosing was tested with 253 pediatric subjects between 1 month and 13 years of age. A smaller study in pediatric patients age 1 month to 3 years compared dosing of 40 mg/kg/day gabapentin (N=38) with placebo (N=38) in patients who were receiving at least one marketed antiepileptic drug and had at least one partial seizure during the screening period, and this study showed no difference between product and placebo (Scientific Information, Teva Canada Ltd. https://www.tevacan-ada.com/globalassets/canada-ph2/product-monographs/teva-gabapentine-capsules-100-300-400-tablets-600-800mg_pm.pdf, accessed June 1st, 2020 and Product Information, Pfizer Canada Inc. https://www.pfizer.ca/sites/default/files/202005/Neurontin_PM_E_237475_2020.05.05.pdf accessed on June 1st, 2020).

The evidence base supporting the use of gabapentin for pain and irritability in infants and children with neurological impairment rests on case series publications describing a limited number of retrospective cases. ⁴¹⁻⁴⁹ The lack of prospective, randomized studies, even for this commonly-used medication, underpins the rationale for this study.

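### The wean-off route for children already on gabapentin is meant for analgesic use, but neither its entry condition nor any exclusion keeps out a child who takes the drug partly for seizure control

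*Protocol*

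**What the plan says.** Protocol section 3.3 (Dose Escalation) opens the topic with background: "Some children with PIUO and SNI have been given gabapentin empirically by their health care provider". It adds that the drug is often kept on without a close look at benefit, and compares its safety with that of other analgesics. The sentence that grants entry then reads: "If a subject is currently on gabapentin at the time of enrolment, and the parent/caregiver wants an evaluation of its effectiveness". If both conditions are met, then after enrolment and consent "the subject will be weaned off of gabapentin, in a stepwise manner with 25% reductions in dose every 3rd day". Once off the drug, the child is randomized like everyone else.

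Section 3.2 lists ten exclusions: allergy, another experimental pain study, poor medical risk, pain explained by the PIUO Pathway, Pain Survey A or B, active nociceptive pain, and renal, hepatic, ECG and sickle cell criteria. The nearest to this point is number 3: "Patients who are a poor medical risk because of other systemic diseases or active uncontrolled infections".

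Section 2.1 shows that the authors know the drug's other use. By the US label, "gabapentin is indicated for adjunctive therapy in the treatment of partial onset seizures", from age 3. It also reports that "Gabapentin was tested in 118 pediatric patients age 3 to 12 years with epilepsy". In Canada the drug is authorized only for adults, "as an antiepileptic agent and is not indicated for use in children".

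Under Gabapentin Risks and Precautions, section 3.3 describes the eligibility criteria as ensuring that "participants who have underlying characteristics that potentially increase their risk for an adverse outcome are excluded".

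**The concern.** The entry sentence asks only whether the child is on gabapentin and whether the caregiver wants it evaluated. It does not ask why the child takes it. A child with severe neurological impairment and unexplained pain may be on gabapentin for two reasons at once, pain and seizures. That child fits the pain-focused lead-in, meets the entry condition, and meets no listed exclusion.

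What is at stake is patient safety. A drug that contributes to seizure control could be withdrawn so that its effect on pain can be tested. The protocol names convulsions only in section 3.12, as an example of an event that may count as serious. That rule acts after the event and does not prevent it.

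**Working it through.** There is no sample size, power or error rate to recompute. The check is a reading of the rules, then a count of days.

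**Step 1. Does any rule stop the wean?**

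- Entry sentence (3.3): two conditions, no indication named.
- Lead-in (3.3): describes some children. It shows intent but sets no condition, and it does not remove a child with both uses.
- Exclusions 1 to 10 (3.2): none mentions seizures, epilepsy or gabapentin used as an antiepileptic.
- Screening items (3.8): age, GMFCS, CFCS, pain score and pain identification. None concerns the reason for a current prescription.
- Baseline Visit (3.8): current medicines are listed with dose and start date. The reason for use is not among the items named.
- Records review (3.8): done before the Baseline Visit. The wean comes after enrolment and consent and before randomization (3.3). The text does not fix which of the two comes first.
- Table 3 footnote (6.2): for a child who took part in the PIUO Study in the last six months, the health information is carried over and only an update is needed.
- Withdrawal in the participant's best interest (3.8): available, but discretionary and not specific to this case.

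No rule in the text shown acts on the reason for use. The Eligibility Assessment and Health Information Form (Appendices 1 and 4) are not shown and may record it.

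**Step 2. How long would such a child be without the drug?**

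Inputs:
- Each period lasts 25 days (6.2, Trial Design Summary).
- Both active dosing tables in 3.3 give zero dose on days 24 and 25, so 2 days.
- The placebo table gives zero dose on all 25 days.
- The washout is 3 days with neither drug nor placebo (6.2). The footnote to the dosing tables can instead be read as making day 26 the first day of period 2, with no days added.

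Longest unbroken zero-dose run:
- Placebo first: 25 days with no added washout; 25 + 3 = 28 days with it.
- Gabapentin first: 2 + 25 = 27 days with no added washout; 2 + 3 + 25 = 30 days with it.

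Total in-trial zero-dose time:
- Placebo first: 25 + 2 = 27, or 25 + 3 + 2 = 30. The last 2 days fall at the end of period 2.
- Gabapentin first: 2 + 25 = 27, or 2 + 3 + 25 = 30.

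The total is therefore 27 or 30 days in either order; only the longest run differs by order.

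**Step 3. The wean itself.** If each 25% cut is of the starting dose, the child spends 3 days each at 75%, 50% and 25%, which is 9 days, and then reaches zero. If each cut is of the current dose, 0.75³ = 0.42 of the dose remains after three cuts and 0.75⁴ = 0.32 after four, so 9 days is the shorter reading. The wean comes before the zero-dose days counted above.

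**The case against.** The strongest reply is that the sentence should be read with its paragraph. The lead-in speaks of empirical use and other analgesics, and the trial measures effectiveness by a pain score, so the evaluation a caregiver can ask for is of pain benefit. This largely stands for a child who takes gabapentin only for seizures. A reader might infer that the protocol opens a route for such children; the paragraph does not support that. It does not settle the case of a child who takes the drug for both reasons.

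Second, the group may not exist. Seizure use in children is off-label in Canada, recruitment is confined to British Columbia (3.7), and the target is 10 children. This also stands: the documents show no such child. But off-label use is not excluded use, since the pain use under test is outside the Canadian authorization too.

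Third, judgment is built in. The wording permits entry and does not compel it. Records are reviewed, exclusion 3 covers poor medical risk, investigators must know the product monograph (4.1), other medicines may continue (3.3), the US seizure indication is adjunctive, and adverse events are recorded from enrolment (3.12). Together these make an unconsidered wean less likely. None of them names seizure control or prevents the wean, and Tables 3 and 4 show no contact before Day 1 of period 1.

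Fourth, the description of the eligibility criteria in the risk section is general and does not promise to list every risk. That is fair. It is best read as the aim that the criteria should serve, and the gap is not a contradiction of it.

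**Conclusion.** The gap is real but narrow. As written, the wean-off route does not exclude a child who takes gabapentin partly for seizure control. Such a child could be weaned to zero and then have a longest zero-dose run of 25 or 28 days (placebo first) or 27 or 30 days (gabapentin first), with 27 or 30 zero-dose days in total in either order.

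These figures assume that the child completes both periods on the tabulated schedule and that period 1 starts directly after the wean. They stop at the end of period 2. The pairs reflect the unsettled question of whether the washout is additional.

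Two stronger readings should be resisted. The day counts do not measure harm: the documents give no seizure risk on withdrawal, and the number of such children may be zero. Nor does the gap bear on any estimate, endpoint or analysis. It is a cheap improvement for patient safety.

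**What to change.** 1. Section 3.3: limit the wean-off route to children who take gabapentin only for pain or irritability.
2. Section 3.3 or 3.8: state that the reason for use is confirmed from the medical-records review already planned, before any wean starts. Apply this also to children whose health information is carried over from the PIUO Study.
3. Section 3.2: add a matching exclusion for gabapentin taken wholly or partly for seizure control. An acceptable alternative is to allow entry only if the physician managing the seizures agrees to the wean and to the placebo period.

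The cost is one sentence each in 3.2 and 3.3 and one clause on timing. The downside is possibly slightly fewer eligible children; the protocol gives no count from which to size that loss. Because the change matches the evident intent of the paragraph, few if any intended participants should be lost.
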